**Table 2: COM-B constructs, determinants of medication adherence, and proposed PT4A intervention components**

COM-B Construct	Determinant of Adherence	PT4A Intervention Components
Capability	Physical (Micro)	
 
How and when to take medicines
 
Pill burden
 

	Psychological (Micro)	
 
Individual knowledge about medicines, hypertension and adherence necessity
 
Understanding the relationship between adherence and clinical outcomes
 

Opportunity	Social (Macro)	
 
Social norms about hypertension and treatment
 
Social support for adherence
 

	Physical (Macro)	
 
Time, ease, and cost of transport to acquire refill
 
Availability and price of medications
 
Opportunity cost of acquiring refill
 

Motivation	Reflective (Micro)	
 
Individual barriers and facilitators of adherence
 
Individual beliefs about hypertension and medicines
 
Patient activation in his/her care
 

	Automatic (Micro)	
 
Habits/Medication routines
 
Emotional response to disease and medicines
 

improve patient activation (e.g. coaching patients to raise concerns and questions with clinicians), and provide psychosocial support. HIT will augment peer roles through the decision support system, teleconsultation functionality, and provision of patient-specific adherence summaries for targeted counseling. The HIT platform will also provide enhanced supply chain analytics in order to optimize availability of medications at the rural dispensing facilities.

### **Aim 1: Identify micro- and macro-level contextual factors that might influence the implementation of the PT4A strategy.**

We will use qualitative research methods to conduct a thorough baseline contextual assessment of barriers and facilitators for implementing PT4A.

Participants: We will conduct focus group discussions (FGDs) of 6-10 participants each among four different groups in each county

: individuals with hypertension (men and women separately), clinical staff, and community members (12 total FGDs). Purposive sampling will be used to select study participants in order to sample a diversity of stakeholders. For individuals with hypertension, diversity of age and distance from the nearest health facility will be targeted. In addition, we will conduct four key informant interviews (KII): one each with the County Executive Committee representative or the county health director for medical services in each of the three counties where we will conduct our study, and one with the head of the division of NCDs at the MOH.

**Methodology: Focus Group Discussions:** Clinical staff will be recruited by identifying staff who care for patients with hypertension. Patients will be recruited from the health facilities participating in the study. We will work with the AMPATH leadership to identify local community members. FGD guides will be created specific to each target group, based on the COM-B constructs listed above (Table 1). Additionally, the FGDs of the clinical staff will assess organizational readiness for change (change efficacy, change commitment, and organizational context) to implement a new multi-level strategy. Each guide will be pilot-tested on three individuals (male, female, and clinician) and revised accordingly. A trained moderator will lead each FGD and facilitate the discussion, with an observer and a note-taker present. Each FGD will last approximately 60 to 90 minutes and will be audio-recorded. We will encourage interactions between and among group members employing participatory techniques that elicit emotional elements and promote group interactions. After each FGD, the facilitators will conduct a debriefing session to summarize findings, compare impressions, identify procedural problems, and develop plans for future FGDs

**Key Informant Interviews (KII):** The four key informants will be approached and recruited in collaboration with AMPATH CDM who have existing relationships with policymakers at both the national and county level. A trained research assistant will conduct each of the KII. Each KII will last approximately 30-45 minutes and will be audio-recorded. We will prepare and pilot-test an interview guide in a similar manner as above and revise it accordingly. In addition to asking about facilitators, barriers and contextual factors that may impact the strategy, the KII will also assess governmental readiness for change to implementing a new multi-level strategy. For all qualitative sessions, a transport allowance and refreshments will be provided to participants.

Focus Group Discussions and Key Informant Interviews will be conducted in-person by the Principal Investigator (PI), [name], or designated research team members, assisted by an interpreter. The study team will adhere to the COVID-19 regulations during the interviews including social distancing, wearing masks throughout the interviews, as well as sanitize and ensuring proper aeration. During the interview, the investigators will ask questions regarding incorporating health IT and peer delivery for improving medication adherence and control of blood pressure among hypertensive patients in PT4A participating communities.

**Outcomes and Analysis:** All FGDs and KII audio-recordings will be transcribed and translated into English by the research team, and all translated interviews will be double-checked for accuracy. We will perform content analysis of the transcripts and notes using NVIVO software. Specific quotations, group interactions, and observations will be assigned codes based on content. Two co-Is will code two transcripts independently, after which they will compare codes, arrive at consensus, and develop a coding list with definitions for the remaining transcripts. In order to assess inter-coder reliability, we will randomly select 10% of transcribed pages to be coded by two co-Is, and the Kappa-statistic will be calculated. Discrepancies will be adjudicated by a third qualitative research co-I. We will then search the remaining transcripts for the following deductive (*a priori*) codes: (a) perception of adherence to hypertension medication; (b) perception of HIT; (c) perceptions regarding the role of social support; (d) perception of peer delivery; and (e) factors that may impact the success of the PT4A strategy. Significant inductive

(emerging) codes will also be identified, assessing for differences by sex. Coded items will be grouped into a hierarchical, branching structure in which broad concepts are first identified. Then themes and interpretive ideas emerging from those constructs are labeled using constant comparison techniques, and subsequently synthesized using matrices structured by the main themes of the analysis. Findings from the FGDs and KIIs will inform the HCD strategy refinement (Sub-Aim 1.1).

**Limitations and Alternative Strategies:** We may have trouble recruiting for the FGDs. To mitigate this, we will adhere to the principles of community engagement as described above, and hold sensitization sessions among potential participants. Given our success recruiting for similar research recently, we do not anticipate that this will be a significant issue. It is also possible to assess for these factors using a more quantitative approach. However, using the proposed type of qualitative methods, our team has successfully uncovered novel factors that have informed and impacted the implementation of previous strategies. It is possible that we will identify factors that are not aligned with the planned components of the PT4A strategy; in this scenario, we will incorporate those factors into the human-centered design approach described in Aim 2.

[figure not shown]
**Aim 2: Use a human-centered design approach to refine and adapt the PT4A strategy (to be implemented following completion of Aim 1 activities)**

We will pursue a participatory, iterative design process and assemble a human centered design (HCD) team consisting of individuals representing stakeholder groups: research team, clinicians, pharmacists, peers, and patients with hypertension, informatics staff, and other providers involved in hypertension care. The design process will involve three phases: brainstorming, conceptualization, and creation. During brainstorming, the facilitator will review relevant information on adherence to hypertension medications, findings from Aim 1, and the PT4A prototype core principles and characteristics. In the conceptualization phase, the team will evaluate advantages and disadvantages of ideas resulting from brainstorming, and arrive at consensus regarding importance, feasibility, and congruence to the PT4A strategy goals, in order to more concretely refine the strategy. In the creation phase, we will develop the refined PT4A strategy. Educational (for patients) and training (for peers) materials will be developed in English, Kiswahili, and other local languages as appropriate, using standard approaches to translation and back-translation.

Core components of the PT4A strategy will include a HIT component and a peer delivery component. Prototype characteristics of each are described as follows (Figure 3).

**Health Information Technology:** All of the HIT components will build upon, and be aligned with, the AMPATH Informatics infrastructure that has been established. We are working with leadership of the AMPATH Informatics program to ensure full alignment. Our PT4A intervention will augment AMRS to support peer-based delivery in four ways: 1) decision support and tailored adherence counselling: provide a patient-level and historical adherence summary that includes pill count, self-report, and clinical data synced with AMRS to generate tailored adherence counselling; 2) teleconsultation: facilitate teleconsultation via text or phone call between peers and clinicians; 3) tracking and accountability: provide timely prompts to peers when refills are near due, and capture participant signature to confirm receipt of medications to improve accountability; and 4) analytics:

**Figure 3.** Summary of the PT4A components

patient-level medication use analytics to predict future stock requirements for pharmacy supply chain. The specific design and implementation of the above will be iteratively improved via the participatory design process, as described in Sub-Aim 1.1. Each peer will be equipped with a tablet loaded with the AMRS-POC software and specific encounter forms and other features associated with the HIT component of the PT4A intervention. A Programmer will be hired as part of the Research staff, in coordination with the AMPATH informatics Program and approval by the Moi Research and Sponsored Projects Office and they will provide

technical support and training for the peers.

**Peer Delivery:** This component will involve trained and paid peer-delivery agents who will cover a prescribed catchment area associated with each health facility in the intervention arm. Peers will play three roles: 1) Drug delivery: peers will deliver medication refills to the patient at a convenient location and time. Upon enrollment, clinical data from the AMRS, including the participant's current prescription and the next refill date, will be sent by AMRS to the pharmacy staff, in order for them to package the medication. Each patient's prescriptions will be individually packed in standard manufacturer-issued blister packs, which will be packaged in single-seal bags to prevent pilferage. A prompt will also be sent by AMRS to the peer, who will confirm with the patient delivery details (which drugs, quantity, location, date, and time for delivery). The peer will pick up the medication package from the pharmacy at the health facility and then deliver the medication to the patient, who will confirm receipt by digitally signing on the HIT tool. The peer will then request the next installment of medications from the pharmacy (via AMRS), accounting for any pills that the patient did not consume and are remaining in the blister pack. The peer will continue this cycle of medication delivery until the patient returns to the health facility for a follow-up clinic visit, when a new prescription will be issued by the clinician to the patient. The peer will then start a new prescription refill cycle for the patient. 2) Psychosocial support and adherence counseling: leveraging the peer-patient relationship, and using the HIT-generated adherence data, the peer will provide adherence counseling and psychosocial support to patients at the time of medication delivery to address individual-level adherence barriers and any new issues that may have been discovered during Aim 1 activities. Peers will be trained in motivational interviewing, health coaching, and psychosocial support. 3) Enhance patient activation: peers will use health coaching strategies to address concerns regarding medications, hypertension and other NCDs, and relationship with clinicians, thereby enhancing patient activation. Training, mentorship, supervision and monitoring of clinicians and peers on clinical content will be performed by the clinician investigators on the study who are qualified to do so,

complemented by the standard CDM training that is organized by CDM leadership and clinicians. Research assistant led training and supervision of peers will be limited to research related SOPs and other research content.

## **Sub Aim 2.1: Evaluate The Intervention For Acceptability And Appropriateness.**

*This will be implemented following completion of Aim 2 activities and analysis*

## **Sub Aim 2.2: Conduct A Pilot of the Intervention and Evaluate Feasibility.**

We will also conduct a pilot of the strategy for up to **1-year** and conduct further FGDs to evaluate feasibility. We will select three pilot health facilities, one from each county. We will hire one peer delivery agent per facility, train them in core roles and responsibilities, and equip them with

tablets. Each peer will be stationed at a specific health facility and will be able to communicate directly with the clinicians, pharmacy staff, and patients. To maintain patient confidentiality, all research

Table 3: Acceptability, Appropriateness, and Feasibility of the PT4A Intervention	
	Outcomes
Acceptability	

• Satisfaction with the proposed intervention design

• Expressed interest or intention to participate

Appropriateness	

• Perceived relevance of intervention to address adherence

• Perceived fit within existing community and clinical infrastructure

Feasibility	

• Anticipated success of implementing intervention in this setting

• Perceived ease of implementing the intervention

staff and peers will receive study specific training on the need to at all times maintain participant confidentiality, in addition to receiving training in good clinical practice (GCP) and human subjects' protection (HSP) training. The HIT platform builds on the AMPATH OpenMRS system which encompasses patient data protection measures such as restricted access to authorized users only, which will further maintain patient confidentiality. We will recruit **up to 100** patients from among these three facilities, targeting an equal number per county. In case there is a report of an adverse reaction to medications or new symptom by the participant to the peer during the pilot phase of the study, all peer navigators will be guided by a decision support system built into the HIT that will require the prompt notification of one of the two local pharmacist investigators in the study, as well as the patient's clinician. The peer will contact directly both the pharmacist investigator(s) and the appropriate clinician. Swift action will be taken based on the advisement of the clinician. Inclusion criteria will include age greater than 18 years, and currently enrolled in the AMPATH CDM program. Exclusion criteria will include acute illness requiring immediate medical attention, terminal illness, or inability to provide informed consent.

We will collect data through a survey on process and implementation measures such as completeness of the peer delivery, satisfaction of the patients, patient activation, and fidelity of delivery strategy. We will conduct FGDs with patients and clinicians then conduct KII (Key informant interviews) with the peer delivery agents, focusing on contextual issues impacting implementation, suggestions for modifications, and concepts of feasibility (Table 3). The target group size for the FGDs is 6-10 participants but if there are insufficient numbers, we will accommodate a smaller size. FGD transcripts, data management, and analysis will be performed as described above. We have used this approach previously with success.

We will evaluate the impact of the pilot on absolute mean change in SBP and medication adherence from baseline to **up to 1 year**. The primary adherence outcome is the pill count adherence ratio, which is the proportion of prescribed doses taken over a 1-month time period, assessed at the end of the pilot. The primary implementation outcome is fidelity, measured as quantity and quality of intervention delivery as intended, comprised of three components: confirmed medication delivery documented by patient e-signature, peer completion of the HIT form, and quality of data entry into the HIT form.

We will also create a retrospective comparator group of CDM patients, by querying AMRS, matched by sex, age, location and by initial blood pressure level. We will use their recorded blood pressure over time and compare the 3, month, 6 month and 1 year change in blood pressure to those of the patients receiving the PT4A intervention to evaluate the magnitude and variance of the intervention effects.

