## PROTOCOL SYNOPSIS

Title:	Peers and Technology for Adherence, Access, Accountability, and Analytics (PT4A) – A Qualitative Study
Grant Number:	1R56HL150036
Study Description:	
The overall objective of this project is to utilize the PRECEDE-PROCEED framework to conduct transdisciplinary, translational implementation research focused on improving medication adherence for hypertension control. The central hypothesis is that peer delivery of medications integrated with HIT (PT4A) will be effective in improving hypertension medication adherence, contributing to improved blood pressure among patients with uncontrolled hypertension in western Kenya. This application will focus on the critical formative components of the overall implementation research objective, and we propose the following specific aims:
 
Aim 1 will identify micro- and macro-level contextual factors that might influence the implementation of the PT4A strategy (individual, family, clinician, health system, and environment), using qualitative methods. Aim 2: We will then use a human-centered design approach to refine the PT4A intervention using the findings from Aim 1. Sub-Aim 2.1 will evaluate the intervention for acceptability and appropriateness by use of a survey tool with patients, peers, and clinical staff. In Sub-Aim 2.2, we will then conduct a pilot of the intervention and conduct a survey questionnaire with patients, peers, and clinical staff to evaluate feasibility. We will evaluate impact on systolic blood pressure, medication adherence, and fidelity of implementation. We will also create a retrospective comparator (control) group of CDM patients, through querying AMRS, matched by sex, age, location and initial blood pressure level. We will then use their recorded blood pressure over a comparable period of upto 1 year and to allow for comparison to the blood pressure changes observed in the patients enrolled in the PT4A program to help understand the magnitude and variance of the intervention effects.

Objectives*:	The overall objective of this proposal is to utilize transdisciplinary, translational implementation research, guided by the PRECEDE-PROCEED framework, to address the challenge of hypertension medication non-adherence in low-resource settings.

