Study Population:	
Approximately 146 individuals will participate in this study. The number is approximate because for focus group discussions, the number of participants can range from 6-10.
 
Aim 1:
 
 
• Focus group discussions (approximately 96 participants): Participants will be patients with hypertension who are currently enrolled in the AMPATH CDM program, and at least 18 years of age from the counties of Bungoma, Trans Nzoia, and Uasin Gishu in Western Kenya. Clinical staff in the AMPATH CDM program and community leaders from the counties will also participate. (12 total FGDs, 6-10 participants each)
 
• Key informant interviews (4 participants): Participants will be County Executive Committee representatives for health from the three Counties included in the study and the Ministry of Health head for non-communicable diseases (NCDs).
 
 
Aim 2:
 
 
• Human Centered Design Team (20 participants): Participants will be individuals representing the following stakeholder groups: research team members, clinicians, pharmacists, peers, patients with hypertension, representatives from the informatics team, and other relevant staff members involved in hypertension care
 
 
Aim 2.1:
 
 
• Use of Survey tools adapted from acceptability and appropriateness measures (39 participants):
 
• Participants will be patients (as described above), peer navigators, and clinical staff (as described above).
 
 
Aim 2.2:
 
 
• Pilot (up to 100 participants): Participants will be patients who are currently enrolled in the AMPATH CDM program, and at least 18 years of age from the counties of Bungoma, Trans Nzoia, and Uasin Gishu in Western Kenya.
 
• Retrospective comparator group: AMRS records of up to 100 patients who will serve as a control group matched by sex, age, location and initial blood pressure level
 

Phase* or Stage:	N/A
Description of Sites/Facilities Enrolling Participants:	AMPATH catchment area in three counties of western Kenya: Bungoma, Trans Nzoia, and Uasin Gishu.

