AMPATH has used the AMPATH Medical Records System (AMRS), a customized version of OpenMRS, since 2005. In 2016, AMPATH developed a software program called “Point-of-Care” (AMRS-POC), which we started using in CDM clinics for hypertension management in 2017. We have developed software modules for the following clinical functions: 1) historical patient data review (patient dashboard); 2) real-time clinical data entry (customized interactive forms with skip logic); 3) decision support tailored to the type and training of clinician (e.g. when to escalate hypertension therapy); 4) health facility management (scheduling, follow-up of patients missing clinic visits, generating administrative reports); and 5) data visualization (quality indicators). AMPATH has invested in a Wi-Fi network and solar power system to ensure network access and server connectivity for each health facility. Our current system is being

implemented in over 30 health facilities serving a patient population of nearly 100,000 patients, and has been used for more than 1 million clinical encounters. We have developed and implemented a HIT-based home glucose monitoring program that has led to significant improvements in glycemic control. We have also implemented real-time interactive HIT for oncology, enabling specialists at the referral hospital to co-manage patients with clinicians from remote health facilities. Finally, we are developing a personal health record platform to support asynchronous telemedicine. The proposed HIT component of this study builds upon this established infrastructure.

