### **Preliminary Data.**

**Suboptimal Medication Adherence.** Adherence to hypertension medications is suboptimal in western Kenya, and there remain gaps to improve patient-level access and medication refill rates. Preliminary analysis of data from participants in the BIGPIC trial (R01HL125487) indicates that nearly 50% of patients with hypertension and/or diabetes reported suboptimal adherence, similar to other countries in Africa. Due to limited cash supply, patients often choose to fill only a part of their prescription on the day of the clinic visit, and are expected to return for refills. AMPATH pharmacy data indicate that as the prescription duration increases, fewer patients fill the prescription for the entire period: 43% filled their 60-day prescription, and only 21% filled their 90-day prescription. The remaining patients required a return visit to refill their prescriptions. However, missed refills are frequent; in fact, 62% of hypertensive patients in this region reported having missed or skipped a refill, while 64% reported having run out of medication before the next refill date. Pharmacy program data confirm this self-report; a recent audit indicated that only 24% of individuals who were due to return to clinic for a prescription refill actually did so.

**Figure 1.** Study sites in western Kenya

the health facility have also been reported as significant barriers. Preliminary analysis of BIGPIC trial data indicates that time taken to reach the health facility is significantly associated with a missed prescription; round-trip estimates average approximately 90-120 minutes. In addition, patients spend nearly two hours at the health facility when attending a hypertension clinic, or even just for a medication refill. We have previously reported that the clinician-patient encounter averages less than 10 minutes, indicating long wait times and therefore time lost from work. To supplement the substantive preliminary data summarized above, we propose to conduct a more thorough assessment of the various factors that might impact successful implementation of the PT4A strategy.

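### The 3-, 6- and 12-month blood pressure comparison depends on who happens to have a reading, and nothing in the plan makes that comparable between pilot and comparator patients

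*Combined protocol and SAP*

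**What the plan says.** Section C, Sub Aim 2.2, creates the comparator from existing records: "We will also create a retrospective comparator group of CDM patients, by querying AMRS". Matching is on sex, age, location and initial blood pressure. The outcome is then defined: "We will use their recorded blood pressure over time and compare the 3, month, 6 month and 1 year change in blood pressure". The stated purpose is to learn the magnitude and variance of the intervention effect. The Protocol Synopsis describes the data as "recorded blood pressure over a comparable period of upto 1 year" and the size as "AMRS records of up to 100 patients who will serve as a control group", alongside up to 100 pilot patients. No visit windows are given.

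On the source of readings, Section C (Setting) describes AMRS point-of-care software, "which we started using in CDM clinics for hypertension management in 2017". For pilot patients, Sub Aim 2.2 and Appendix A name the mean change in SBP as an outcome but do not say who measures it, where or when.

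The only missing-data provision is in the Milestones table, in the row for the pilot analysis. It promises an algorithm before data collection and gives no content.

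On attendance, Preliminary Data reports that "only 24% of individuals who were due to return to clinic for a prescription refill actually did so". Under Aim 2, Peer Delivery, "The peer will continue this cycle of medication delivery until the patient returns to the health facility for a follow-up clinic visit", at which point the clinician issues a new prescription.

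**The concern.** A patient who does not attend leaves no reading. If change is computed from whatever is recorded, each group's mean describes only its members with a follow-up value, and those members probably differ from the rest in treatment-taking and in SBP change. This would matter less if the same process produced readings in both groups. Here one group's readings come from routine encounters and the other's from an unstated process. Matching ignores visit frequency and retention, so it does nothing to align them.

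What is at stake is the effect size itself. The comparator exists to supply it, and the pilot is formative work for a planned cluster-randomized trial. A distorted magnitude could carry into the planning of that trial.

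**Working it through.** The plan states no power, precision or bias figure for this comparison, so there is nothing to reproduce. The calculation below is an illustration on declared assumptions.

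**Inputs.**
- r1, r0: shares of pilot and comparator patients with a reading in a given window. Neither is in the documents. Assumed 50% to 100%.
- D: the mmHg by which SBP falls more in patients with a reading than in those without, taken as equal in both groups. Not in the documents. Assumed 2, 5 or 10.
- Scale: the earlier peer-delivery pilot in Preliminary Data reported a fall of nearly 6 mmHg.

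**Formula.** In a group with share r, the whole-group mean fall is r × (fall with a reading) + (1 − r) × (fall without). The mean among those with a reading therefore exceeds the whole-group mean by (1 − r) × D. With no true effect, the comparator's observed fall exceeds the pilot's by

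(1 − r0) × D − (1 − r1) × D = (r1 − r0) × D.

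A positive value makes PT4A look worse than it is; a negative value makes it look better.

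**Results (mmHg).**

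| r1 (pilot) | r0 (comparator) | D = 2 | D = 5 | D = 10 |
|---|---|---|---|---|
| 80% | 50% | 0.6 | 1.5 | 3.0 |
| 50% | 80% | −0.6 | −1.5 | −3.0 |
| 100% | 80% | 0.4 | 1.0 | 2.0 |
| 100% | 50% | 1.0 | 2.5 | 5.0 |
| equal | equal | 0 | 0 | 0 |

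First row: (0.80 − 0.50) × 2 = 0.6 and (0.80 − 0.50) × 10 = 3.0. Against 6 mmHg that is 0.6/6 = 10% to 3.0/6 = 50%. The rows with 100% are the case in which the study measures every pilot patient.

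The sign also changes if D is negative, for example if patients who are doing badly attend more. If D differs between groups (D1 pilot, D0 comparator), the artefact is (1 − r0) × D0 − (1 − r1) × D1, which need not be zero even when the shares are equal.

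**Sampling error for comparison.** Treating the groups as independent and assuming an SD of change of 20 mmHg, the 95% half-width is 1.96 × 20 × √(1/100 + 1/100) = 5.5 mmHg with 100 readings each. With 80 and 50 readings it is 1.96 × 20 × √(1/80 + 1/50) = 7.1 mmHg. For SDs of 15 and 25 the pairs are 4.2 and 5.3, and 6.9 and 8.8. Sampling error is thus larger than the artefact in the first row, but the interval makes no allowance for the artefact.

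**The case against.** The strongest reply is that this is a supporting comparison in a pilot. The primary outcomes are the pill count adherence ratio and fidelity, and a randomized trial is to follow. All clinical data pass through AMRS, a missing-data algorithm is promised, and the plan nowhere says that it will choose comparators for having a later reading or analyse only complete pairs. This limits the weight of the point. It does not answer it: the algorithm has no content, and without a stated rule the natural reading of the text is an observed-case comparison.

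Three stronger readings are tempting, and the documents do not support them.

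- *Peer delivery removes the visits at which blood pressure would be taken.* Delivery replaces refill trips, but clinician follow-up visits continue. Preliminary Data names a refill-only visit separately from a hypertension clinic visit, and nothing says that blood pressure is measured at the former. Peer support could also raise clinic attendance.
- *The bias runs towards no effect.* That needs a higher share with readings in the pilot group and a positive D. Neither is documented.
- *The 24% is the share of comparators with a reading, so the bias could match the earlier pilot's whole effect.* It is a refill-return rate. It shows that attendance is a real problem in this setting but does not measure how often blood pressure is recorded.

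It is also not established that pilot readings come only from clinic attenders. If the study measures everyone enrolled, the contrast is comparators with an encounter against all pilot patients. That is still unequal, though in a different way.

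**Conclusion.** The point holds as a gap in ascertainment. Comparator follow-up blood pressure depends on a recorded encounter, the source and timing of pilot SBP are not stated, and neither matching nor analysis makes the two comparable. The resulting error is about (r1 − r0) × D, or 0.6 to 3.0 mmHg at 80% against 50% with D of 2 to 10. It has the opposite sign if the shares are swapped, and is zero if the shares and D are equal. The shares and D are assumptions, so these figures show scale and are not bounds. The direction is unknown. The plan should be changed, because the comparison is meant to yield a magnitude and the remedy is cheap. The primary outcomes are not affected.

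**What to change.** In Section C, Sub Aim 2.2, and in the matching parts of the Synopsis and Appendix A:

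1. Select comparators on index-visit data only, never on having a later reading. Add prior visit frequency from AMRS as a matching or adjustment variable.
2. State where and when pilot SBP is measured. Base the between-group comparison on the same type of reading (AMRS clinic-recorded) in the same pre-set windows around 3, 6 and 12 months. Keep any study-measured pilot readings for the within-group change, so that none are discarded.
3. Analyse all available readings in a repeated-measures mixed model with group × time and baseline SBP as covariate, accounting for matched set. This replaces change among those with both values.
4. Report the share with a reading by group and window. Add one sensitivity analysis weighted for attendance, because the mixed model assumes that readings are missing at random.
5. Reconcile the pilot's length. Appendix A (Subaim 2.2, Methods) gives 3 months, while Sub Aim 2.2 in Section C gives up to 1 year. A 3-month pilot would leave no 6- or 12-month pilot comparison.

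The cost is a revised AMRS query, revised analysis text and slightly more analysis work. No extra patients or visits are needed. The downside is fewer apparently complete pairs and a possibly less precise estimate.
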